1.4 Nonclinical Data

An overview of the key nonclinical data is provided below. For additional details regarding the nonclinical pharmacology, pharmacokinetic (PK) and toxicology studies conducted to date, refer to the GBT440 Investigator's Brochure (IB).

1.4.1 Nonclinical Pharmacology

In vitro pharmacology studies were conducted to characterize the pharmacodynamic (PD) effects of GBT440. These studies demonstrated that GBT440 binds to Hb, modulates Hb-O₂ affinity and maintains the oxyHb state during deoxygenation. In addition, these studies showed that GBT440-modified Hb retains the Bohr Effect, which is the ability to augment oxygen delivery in metabolically active (low pH) tissues. This should preserve the ability of GBT440-modified Hb to off-load oxygen to metabolically active tissues, despite its increased affinity for oxygen.

In vivo pharmacology studies were performed in murine models of acute hypoxia challenge and pulmonary hypoxemia (lipopolysaccharide [LPS]-induced acute lung injury [ALI] and bleomycin induced lung fibrosis and hypoxemia (Xin 2016)). These in vivo studies demonstrated that pharmacologically increasing Hb-O₂ affinity in these murine models of pulmonary hypoxemia resulted in improved O₂ saturation, translating into improved physiologic endpoints and survival.

1.4.2 Nonclinical Pharmacology

The safety pharmacology studies conducted with GBT440 are summarized in the GBT440 Investigator's Brochure. Safety assessments of GBT440 in 3 in vivo studies did not identify any biologically significant effects in the central nervous system (CNS) and respiratory system. There were minor effects in the cardiovascular (CV) safety pharmacology studies, with a mild increase in systolic BP at higher doses (1000 mg/kg) and a small decrease (15.3%) in hERG channel current at 10 μ M. Based on these results, there appears to be a low risk to humans for adverse effects on CNS, respiratory, or CV function.

1.4.3 Nonclinical Pharmacokinetics

The PK studies conducted with GBT440 are summarized in the GBT440 Investigator's Brochure. PK evaluations showed that GBT440 had low blood clearance (CL), low blood V_{ss}, and long terminal t_{1/2} and was well absorbed in all animal species tested. GBT440 whole blood concentrations were much higher than plasma concentrations (calculated RBC: plasma ratio ~150:1), consistent with a high affinity and specificity of GBT440 for Hb. The PK properties of GBT440 in animals suggest that it will preferentially bind to Hb and be slowly, but completely eliminated from the body. With increasing doses in rats and dogs, the exposure with GBT440 is less than dose-proportional.

1.4.4 Metabolism and Potential Drug Interactions

Metabolism was the major route of elimination of GBT440 in humans. Renal excretion was a minor elimination pathway.

In vitro metabolism studies indicate that GBT440 could be metabolized by several CYP enzymes, i.e., CYP1A1, 1B1, 2B6, 2C9, 2C19, 3A4, and 3A5. However, in total, the data show that the exposure of GBT440 is unlikely to dramatically increase (<1.7-fold) when coadministered with a CYP inhibitor. Refer to [Section 8.5.2](#) for restricted therapies in this study.

GBT440 has also been evaluated as a potential inhibitor/substrate of various membrane transporters. Refer to the GBT440 IB for further details of these studies.

1.4.5 Toxicology

The toxicity of GBT440 has been evaluated in single dose, repeat dose and reproductive toxicity studies. The genotoxic potential of GBT440 has been evaluated in a battery of in vitro and in vivo assays. The details of the nonclinical toxicology program, including toxicokinetics, are provided in the GBT440 IB.

1.5 Clinical Development of GBT440

Clinical studies have been conducted in healthy subjects (including 10 Phase I clinical pharmacology studies) and in patients with SCD and IPF.

The Phase II IPF study (GBT440-006) is a randomized, controlled trial evaluating the safety and PK of GBT440 and its effects on oxygen saturation in IPF subjects who are hypoxemic with exercise. GBT440 is being dosed at 600 mg, 900 mg and 1500 mg orally daily for 28 days.

The Phase I/II study (GBT440-001) is a randomized, placebo-controlled, ascending dose study evaluating the safety, tolerability, PK, and PD effects of single and multiple doses of orally administered GBT440 in healthy subjects and subjects with SCD. Healthy subjects have received multiple doses of 300 mg to 900 mg/day for up to 15 days. SCD subjects have received multiple doses of 500 mg to 1000 mg/day for up to 28 days, and 700 mg or 900 mg/day for up to 90 days; some subjects (900 mg) are continuing treatment for up to 6 months under a separate protocol (GBT440-024).

The Phase III study (GBT440-031) is a randomized, double-blind placebo-controlled study evaluating the efficacy and safety in SCD patients at GBT440 doses of 900 mg or 1500 mg for up to 72 weeks

The Phase II study in adolescent subjects with SCD (GBT440-007) is an open label, single dose and multiple dose PK study of GBT440 in pediatric subjects, ages 12 to 17 years.

Refer to the GBT440 IB for additional details regarding GBT440 development and all clinical studies.

1.5.1 Safety Findings

To date, GBT440 has been well tolerated over a range of doses administered to healthy and SCD subjects, for up to 90 days.

As of 30 September 2016, a total of 259 subjects have received at least 1 dose of GBT440: 205 healthy subjects, 47 adult SCD subjects and 7 pediatric SCD subjects.

In Study GBT440-001, the majority of the adverse events (AEs) were mild or moderate (Grade 1 or Grade 2), most commonly headache or diarrhea, and no clinically significant findings in vital signs, 12-lead electrocardiograms (ECGs), or laboratory safety values were identified.

In the SCD subjects dosed for 90 days, the majority of the AEs were also mild or moderate (Grade 1 or Grade 2). The most common AEs, occurring in ≥ 2 subjects and at a similar frequency in GBT440 and placebo-treated subjects, were headache, back pain, fatigue, and rhinitis.

The AEs that occurred at a higher rate in subjects receiving GBT440 included cough, diarrhea, and rash, of which diarrhea and rash were considered treatment-related by the Investigator. No episodes of anaphylaxis, anaphylactoid, or hypersensitivity reactions were reported.

Rashes were morbilliform in nature, typically involved the trunk or extremities, associated with mild pruritus, resolving within 2 to 5 days (in one case with continued dosing), and were not associated with any systemic features.

Overall, 10 serious adverse events (SAEs) have been reported as of 30 September 2016, in 10 subjects with SCD, considered by the Investigator to be not related to the study drug. There were 7 events of sickle cell crisis (Grade 3), all occurring off treatment during follow-up (1 placebo; 6 GBT440); 1 event of presumed infection with hemolysis (Grade 2) (GBT440); 1 event of an ovarian cyst (Grade 3), occurring after the last dose of study drug (GBT440) and 1 event of Grade 2 upper respiratory tract infection requiring hospitalization (GBT440).

Please refer to the GBT440 IB for additional details on GBT440 safety findings.

1.5.2 Pharmacokinetic Parameters

The mean PK results of GBT440 from analyzed samples to date derived from whole blood concentration-time profiles, shows that both maximum blood concentration (C_{max}) and area under the curve (AUC) increases proportionally with study drug dose for both single or multiple doses in Study GBT440-001. The exposure of GBT440 at steady-state was consistent with accumulation predicted based on the single dose data.

For the same dose, GBT440 exposure was lower and the $T_{1/2}$ was significantly shorter in subjects with SCD compared with healthy subjects. At steady-state, the exposure in subjects with SCD was also lower than that observed in healthy subjects. Since IPF patients will most likely have hematocrit values within the normal range, PK of GBT440 in these patients are expected to be similar to that of healthy volunteers.

Please refer to the GBT440 IB for additional details of GBT440 PK parameters.

1.5.3 Dose Rationale

The selection of the GBT440 doses for this study are based on a benefit risk profile that supports studying the potential efficacy and safety of GBT440 in a population of IPF subjects who have a high unmet medical need.

Based on data from in vivo studies of hypoxemia ([Section 1.4.1](#)) demonstrating a dose-dependent increase in Hb-O₂ affinity (PD effect of GBT440) and PK/PD data from study GBT440-001 the selected doses are expected to increase Hb-O₂ affinity to an extent that will result in a clinically significant increase in oxygen saturation.

The safety of the proposed doses is based on the overall favorable safety profile of GBT440 in studies to date:

- Study GBT440-006 in IPF subjects who desaturate with exercise. The safety findings from 16 subjects in Part A of the study who completed 28 days of dosing (900 mg and 600 mg GBT440) were reviewed by the study's Safety Monitoring Committee who endorsed continuing the study with the addition of a 1500 mg dose arm.
- Safety findings from healthy volunteers, SCD patients and IPF patients have not demonstrated that a daily, oral 900 mg dose of GBT440 represents a maximum tolerated dose (MTD).
- Continued favorable safety profile in ongoing studies evaluating GBT440 in subjects with SCD (refer to [Section 1.5](#)), including continued dosing for up to 6 months.

The safety of the proposed doses is based on the totality of available nonclinical and clinical safety data from IPF and SCD patients.

1.5.4 Potential Risk of GBT440 Treatment

Tissue Hypoxia

There is a theoretical risk of tissue hypoxia in subjects treated with GBT440 based on the mechanism of action and the potential for impairment in O₂ offloading at the tissues. However, in vitro data show that GBT440-modified Hb remains sensitive to the Bohr effect, and in vivo data from animal models of pulmonary hypoxemia are consistent with increased oxygen extraction and consumption by tissues. Furthermore, clinical data from subjects receiving study drug and those participating in maximal cardio-pulmonary exercise tests in the ongoing Phase I/II study, GBT440-001, have not identified a concern with tissue hypoxia. Please refer to the GBT440 IB for further details.

IPF subjects in this study will be closely monitored for subclinical evidence of worsening tissue hypoxia including using assessments for erythrocytosis, increased resting heart rate and erythropoietin and laboratory tests indicating organ injury (e.g., liver aminotransferases).

2 STUDY OBJECTIVES

2.1 Primary Objective

To evaluate the effect of GBT440 on oxygen saturation at rest, breathing room air, on Days 30 and 90 compared to baseline.

2.2 Secondary Objectives

- To evaluate the effect of GBT440 on the requirement for supplemental O₂ at rest and post-exercise at Days 30 and 90 compared to baseline
- To evaluate the effect of GBT440 on resting and post-exercise Alveolar-arterial O₂ tension difference [P(A-a)O₂] at Days 30 and 90 compared to baseline
- To evaluate the effect of GBT440 on 6MWD at Days 30 and 90 compared to baseline
- To evaluate the effect of GBT440 on IPF-related symptoms, using patient reported outcomes (PROs), at Days 30 and 90 compared to baseline
- To evaluate pulmonary function at Day 90 compared to baseline
- To evaluate the safety and tolerability of 900 mg and 1500 mg GBT440 dosed daily for 90 days
- To evaluate the PK of GBT440

2.3 Exploratory Objectives

- To evaluate the effect of GBT440 on the need for any O₂ while at rest at Days 30 and 90 compared to baseline
- To compare the change in O₂ requirement between the two O₂ flow rate allocation groups
- To evaluate the effect of GBT440 on extent of activity during daily living at Days 30 and 90 compared to baseline

3 INVESTIGATIONAL PLAN

3.1 Study Design

This is an open label study that will be conducted in two parts. Together, Parts A and B will provide safety and efficacy data across the two GBT440 doses that are expected to improve oxygen saturation in the enrolled subjects.

Approximately up to 32 eligible subjects will be enrolled in the study.

- In Part A (Figure 1), up to approximately 16 eligible IPF subjects will receive 900 mg of GBT440 administered orally as 3×300 mg capsules or tablets once daily for 90 days.
- In Part B (Figure 1), up to approximately 16 eligible IPF subjects will receive 1500 mg of GBT440 administered orally as 5×300 mg capsules or tablets once daily for 90 days.

Subjects enrolled in Part A will follow the GBT440 900 mg visit schedule. Subject enrolled in Part B will follow the GBT440 1500 mg visit schedule. Schedules of Assessments are provided in [Appendix A \(Table 15-1 for Part A; Table 15-2 for Part B\)](#).

A signed and dated informed consent form (ICF) must be obtained before any study-specific tests may be performed.

[figure not shown]
The screening period for each subject commences when the subject undergoes the first study-specific screening assessment and must be completed and tests evaluated before dosing (Day 1). Subjects may be rescreened up to 2 times, if deemed appropriate by the Principal Investigator. The rescreening visit should not occur sooner than 10 calendar days after the failed screening visit.

After the screening visit, the study includes the following study periods ([Figure 3-1](#)):

[figure not shown]
- Treatment period (90 days): subjects in Part A will receive 900 mg (3×300 mg) and subjects in Part B 1500 mg (5×300 mg) capsules or tablets daily
- Safety follow up (30 days): safety will be assessed for at least 5 half-lives after the last dose of GBT440 in both Parts A and B

Figure 3-1 Study Design

Part A

Part B

Subjects, who discontinue for reasons unrelated to toxicity, may be replaced if:

- the subject does not take at least 80% of their daily doses of study drug, prior to Day 30 (24 days) or Day 90 (72 days)

and/or

- the subject does not take study drug for at least 8 consecutive days prior to Days 30 or 90

The end of the study is defined as the date when the last subject last visit occurs, which is expected to be approximately 120 days after the last subject is enrolled.

This study will be performed in compliance with the protocol, ICH Good Clinical Practice (GCP), and applicable regulatory requirements. Aspects of the study concerned with the Investigational Medicinal Product (IMP) will meet the requirements of Good Manufacturing Practice.

3.2 Endpoints

3.2.1 Primary Endpoint

The primary endpoint is change and % change from baseline in oxygen saturation at rest (SpO₂ or SaO₂), measured while breathing room air, at Days 30 and 90.

3.2.2 Secondary Endpoints

- Change and % change from baseline in O₂ flow rate (L/min), measured at rest, to maintain a target oxygen saturation (SpO₂) of 89 to 92%, at Days 30 and 90
- Change and % change from baseline in O₂ flow rate (L/min), measured post-exercise to maintain a target oxygen saturation (SpO₂ or SaO₂) of 89 to 92%, at Days 30 and 90
- Change and % change from baseline in resting P(A-a)O₂ at Days 30 and 90
- Change and % change from baseline in post-exercise P(A-a)O₂ at Days 30 and 90
- Change and % change from baseline in 6MWD, at Days 30 and 90
- Change in patient-reported IPF-related symptoms from baseline, measured by ATAQ and SGRQ, at Days 30 and 90
- Change from baseline in forced vital capacity (FVC) and diffusing capacity of the lung for carbon monoxide (DLco) at Day 90

3.2.3 Exploratory Endpoints

- Number and % of total subjects no longer requiring O₂ at rest, at Days 30 or 90
- Difference between the two O₂ allocation groups, in the change from baseline in resting O₂ flow rate (L/min), to maintain a target oxygen saturation (SpO₂ or SaO₂) of 89 to 92%, at Days 30 and 90
- Change from baseline in daily activity, measured by a pedometer, at Days 30 and 90

3.2.4 *Safety Endpoints*

The safety outcome measures for this study are the frequency and severity of treatment emergent adverse events (TEAEs) and tolerability of GBT440 administered daily orally for 90 days.

3.2.5 *Pharmacokinetics Endpoints*

Pharmacokinetic (PK) parameters of GBT440 in plasma and whole blood, including but not limited, minimum concentration (C_{\min}) at steady-state.

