8 DOSAGE AND TREATMENT ADMINISTRATION

8.1 Treatment Regimen

GBT440 will be administered orally each day for 90 days. GBT440 will be administered as 300 mg capsules or tablets.

Part A:

- GBT440 900 mg: three 300 mg capsules or tablets

Part B:

- GBT440 1500 mg: five 300 mg capsules or tablets

Instructions for administration of study drug:

- Self-administered by subject in the morning
- May be taken with or without food
- May be taken with water or another non-alcoholic beverage
- Swallow the capsules or tablets whole

Subjects must be instructed not to take study drug on the day of their scheduled visits (refer to the Schedules of Assessments provided in Appendix A [[Table 15-1](#) for Part A; [Table 15-2](#) for Part B]).

Study drug will be administered at the site on these days, after completion of all the assessments scheduled for that visit. The subject should be instructed to swallow the capsules or tablets whole.

If a subject misses a dose of the study drug, they should resume normal dosing the next day; i.e., on the next day, the dose of study drug should be unchanged — not increased or decreased.

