APPENDIX A SCHEDULES OF STUDY ASSESSMENTS

Table 15-1 Schedule of Assessments: Part A — 900 mg Dose

	Screening ^a	Treatment Phase						End of Study (EOS)	Early Term (ET) ^b
	Day -21 to Day -1	Day 1	Day 15 ±3	Day 30 ±3	Day 45 ±3	Day 60 ±5	Day 90 ±5	Day 120 ±5	
Procedures and Assessments	Visit 1	Visit 2	Visit 3	Visit 4	Visit 5	Visit 6	Visit 7	Visit 8	ET
Informed consent ^c	X								
Eligibility assessment	X								
Medical history, demographics, and baseline conditions	X	X ^d							
Concomitant medications	X	X	X	X	X	X	X	X	X
Review adverse events ^c	X	X	X	X	X	X	X	X	X
Complete physical exam ^f	X								
Limited physical exam ^g		X	X	X	X	X	X	X	X
Height	X								
Weight	X			X		X	X	X	X
Vital signs ^h	X	X	X	X	X	X	X	X	X
SpO ₂ ⁱ	X	X	X	X	X	X	X	X	X
12-lead ECG ^j	X						X		X
Urine pregnancy test ^k		X		X		X	X	X	X
Serum pregnancy test ^l	X								
Hematology, serum chemistry, liver function tests	X			X		X	X	X	X
Urinalysis	X					X	X		X
Coagulation	X								
Serum erythropoietin		X		X			X	X	X
PK Blood Samples			X	X		X	X	X	

	Screening ^a	Treatment Phase						End of Study (EOS)	Early Term (ET) ^b
	Day -21 to Day -1	Day 1	Day 15 ±3	Day 30 ±3	Day 45 ±3	Day 60 ±5	Day 90 ±5	Day 120 ±5	
Procedures and Assessments	Visit 1	Visit 2	Visit 3	Visit 4	Visit 5	Visit 6	Visit 7	Visit 8	ET
Spirometry	X						X		
DLco	X						X		
Oxygen titration test ^m		X		X			X	X	
Arterial blood gas ^m		X		X			X	X	
6 MWT ^m		X		X			X	X	
Borg scale ^m		X		X			X	X	
SGRQ ⁿ		X		X		X	X	X	
ATAQ ⁿ		X		X		X	X	X	
Study drug dispensing to subject		X	X	X	X	X			
Study drug administration at site ^o		X	X	X	X	X	X		
Pedometer dispensing to subject		X							

Abbreviations for Table and Footnotes: ATAQ = A Tool for Assessment of Quality of Life; DLco = lung diffusing capacity measured using carbon monoxide; ECG = electrocardiogram; eCRF = electronic Case Report Form; EOS = end of study; ET = early term; 6MWT = 6-minute walk test; PK = pharmacokinetic; PRO = patient reported outcome; SAE = serious adverse event; SGRQ = St. George’s Respiratory Questionnaire; SpO₂ = oxygen saturation measured by pulse oximetry.

Note: All assessments should be performed within the window indicated for each scheduled visit. All assessments should be performed prior to receiving study drug. SGRQ and ATAQ should be performed before all other assessments, followed by 12-lead ECG and then vital signs.

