## 2 INTRODUCTION

This statistical analysis plan (SAP) was prepared in accordance with Protocol GBT440-026, dated 5June2017 (Amendment 2), and was generated prior to locking the study database. This SAP specifies the safety analyses to be performed for an abbreviated report. Planned pharmacokinetic (PK) analyses will be described in a separate analysis plan.

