## **3 STUDY ENDPOINTS**

Endpoints described below are for the safety summaries only.

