### 7.1 Study Day

Study Day 1 corresponds to the date of the first dose of any study drug.

Unless otherwise specified, the timing of all study-related events, assessments, and interventions will be calculated relative to Study Day 1. For events, assessments, and interventions after Study Day 1, study day represents the elapsed number of days from Study Day 1, inclusive:

$$\text{Study Day } n = (\text{Date of assessment} - \text{Date of Study Day 1}) + 1 \text{ day}$$

Study Day -1 will be the day before Study Day 1, and in general for assessments prior to Study Day 1, study day is defined as:

$$\text{Study Day } n = (\text{Date of assessment} - \text{Date of Study Day 1})$$

For listings (such as for adverse events) that include the derivation of “days since last dose,” this is defined as event date – date of last dose. Events that occur on the same day as the last dose of study drug will therefore be described as occurring zero days from the last dose of study drug.

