### 7.2 Baseline

Unless otherwise specified, the baseline value for a given variable is defined as the last measurement for the variable prior to the first dose of GBT 440. For variables where multiple assessments prior to first dose are collected, the average of those assessments is calculated for the baseline value (eg, vital signs).

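### The pedometer is first dispensed on the day of first dose, so the exploratory daily-activity endpoint has no pre-treatment baseline

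*Protocol*

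**What the plan says.** The exploratory objective in Protocol section 2.3 is "To evaluate the effect of GBT440 on extent of activity during daily living at Days 30 and 90 compared to baseline", and the matching endpoint in section 3.2.3 is "Change from baseline in daily activity, measured by a pedometer, at Days 30 and 90".

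The row "Pedometer dispensing to subject" appears in both schedules in Appendix A. It carries a single mark, in the Day 1 (Visit 2) column, and the Screening cell is empty. Table 15-2 (Part B) also lists return of the device at Day 120. Table 15-1 (Part A) has no return row.

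Day 1 is the first dosing day. For visit days, Protocol section 8.1 states: "Study drug will be administered at the site on these days, after completion of all the assessments scheduled for that visit". SAP section 7.1 agrees on the calendar: "Study Day 1 corresponds to the date of the first dose of any study drug".

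The only general baseline rule is in SAP section 7.2: "Unless otherwise specified, the baseline value for a given variable is defined as the last measurement for the variable prior to the first dose". It has no pedometer exception. The SAP limits its own scope. Section 2 says "This SAP specifies the safety analyses to be performed for an abbreviated report", and section 3 says "Endpoints described below are for the safety summaries only".

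**The concern.** Daily activity is measured over whole days of ordinary life. The other change endpoints can be taken within one visit before dosing: the oxygen titration test, arterial blood gases, 6-minute walk, SGRQ and ATAQ on Day 1, and spirometry and DLco at Screening. The pedometer was given the same Day 1 slot as most of these, and for it that slot comes too late.

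This matters because the trial is open label and not randomized (Protocol section 9), and both parts receive GBT440. With no concurrent untreated group, a subject's own pre-dose period is the only possible pre-treatment comparison. If pedometer results were reported as change from baseline, readers would take the reference to be pre-treatment when it could only be a period after dosing had begun.

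**Working it through.** There is no stated figure to reproduce. SAP section 4 says the sample size does not rest on power, and neither document gives a variance or expected effect for this endpoint. The check is a calendar count.

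**Inputs**
- Dispensing day: Day 1 in Table 15-1 and Day 1 in Table 15-2.
- First-dose day: Day 1 (Protocol sections 5.1 and 8.1, SAP section 7.1).
- Screening window: Day -21 to Day -1 (Appendix A and Protocol section 5.3.1).
- Day numbering: Day -1 is the day before Day 1, with no Day 0 (SAP section 7.1).

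**Step 1: the plan as written.** Full pre-dose wear days are the study days lying strictly between the dispensing day and Day 1, or none if dispensing is on Day 1. Dispensing is on Day 1 in both parts, so the count is 0 for every subject.

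**Step 2: the pre-dose hours of Day 1.** The device could be worn at the site between dispensing and dosing. Those hours include the oxygen titration test and the 6-minute walk, both scheduled that day before drug. They do not represent daily activity.

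**Step 3: the SAP default.** Taking the last measurement before first dose needs a pre-dose daily-activity value to select. From steps 1 and 2 there is none.

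**Step 4: other text.** Protocol section 5.5 describes the other disease-related evaluations but has no pedometer procedure: no wear period, valid-day rule, run-in or baseline. The protocol refers to separate manuals for the oxygen titration test, the walk test, laboratory samples and pharmacy, but to none for the pedometer. A manual could not in any case supply wear before the scheduled dispensing date.

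**Step 5: what dispensing at Screening would give.** If the device is given on Day -d, full pre-dose wear days = d - 1.

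| Dispensed on | Full pre-dose wear days |
|---|---|
| Day -21 | 20 |
| Day -15 | 14 |
| Day -8 | 7 |
| Day -1 | 0 |

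A minimum of n full days therefore needs dispensing on Day -(n + 1) or earlier. Moving the mark solves the problem for most of the window but not for a subject screened just before Day 1.

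**The case against.** The strongest reply is that nothing planned depends on this. The endpoint is exploratory, Protocol section 11.3.1 commits only to descriptive summaries of primary and secondary endpoints, and the SAP covers safety for an abbreviated report. That stands, and it limits the weight of the point. It does not remove it, because the protocol still states the objective and endpoint, and the SAP repeats the objective in section 2.4.

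A second reply is that the first days after Day 1 could serve as the reference. Exposure accumulates to steady state (Protocol section 1.5.2), so those days may carry less than steady-state exposure. But the documents define no such window, and it would still be on drug.

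A reader might infer more than the documents support:

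- **That no off-drug wear exists at all.** Part B's Day 120 return may yield wear after the last dose at about Day 90. That would be a post-treatment washout period. It is not a baseline and is nowhere defined as a comparator. Part A lists no return, so how long wear continues there is not stated.
- **That all wear between Day 1 and the Day 30 or Day 90 visit is known to be on treatment.** No wear schedule is given, and Protocol sections 6.3 and 8.3.2 allow dosing to be interrupted or stopped while the subject stays in the study.
- **That the result would favour the drug.** Nothing in the documents lets the direction or size of a bias be derived.

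**Conclusion.** The point holds as a scheduling defect: 0 full pre-dose wear days in both parts, hence no pre-treatment baseline for the pedometer endpoint in any of the up to 32 subjects. The count rests on the column position of one mark in each schedule and on dosing at the Day 1 visit. It needs no assumption about wear, compliance or variability.

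Its reach is small. It touches one exploratory objective and its endpoint, changes no output in the supplied SAP, and becomes material only if pedometer data are reported as change from baseline. The primary, secondary and safety endpoints are unaffected. It is worth considering rather than essential.

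**What to change.** If subjects remain to be enrolled:

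1. Move the dispensing mark from Day 1 to Screening in both tables, after the screening SpO2 check.
2. Define baseline as the mean daily count over the full wear days before Day 1, with a stated minimum number of valid days. The documents offer no figure for that minimum, so the sponsor must choose and justify it.
3. Compare it with windows of equal length before the actual Day 30 and Day 90 visits.
4. State that subjects screened too late to reach the minimum are not evaluable for change. Alternatively, set a minimum screening-to-dose interval within the existing Day -21 to Day -1 window.

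For subjects already dosed without pre-dose wear, report absolute activity, or change from an early reference explicitly labelled as on-treatment, and do not call it change from baseline. Enrolment status is not given. If enrolment is complete, only this labelling applies.

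Costs: a protocol amendment with IRB/IEC approval (Protocol section 12.2), and short text for the baseline, the valid-day minimum, the visit windows and the non-evaluable rule. Some devices will go to subjects who later fail screening or the Day 1 SpO2 check. Some late-screened subjects will have no baseline, which counts with up to about 16 per part. First dose is not delayed unless the optional interval is adopted, and then only for subjects who would otherwise have been dosed soon after Screening.
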